5.2.1.3. Dose Modifications for Vorinostat

Because there may be overlap between vorinostat and MK-3475 toxicities, patients experiencing any Grade 3 toxicity (except those outlined in Table 3.1 and Section 5.2.1.4) or any Grade 4 toxicity will have *both MK-3475 and vorinostat held until improvement of the adverse event to Grade 1 or baseline.*

The following table describes vorinostat dose levels for patients receiving MK-3475 and vorinostat combination *for the phase I portion of the study*, This table will also be used in the Phase II portion of the *study if the Vorinostat dose is determined to be 400mg*.

Starting Dose	1st dose reduction	2nd dose reduction	3rd Dose Reduction
Vorinostat	Vorinostat	Vorinostat	Discontinue therapy
4 capsules – 400 mg	3 capsules – 300 mg	2 capsules – 200 mg	
OR	OR	OR	
8mL of 50mg/ml	6mL of 50mg/mL	4mL of 50mg/mL	
suspension	suspension	suspension	
5 out of 7 days	5 out of 7 days	5 out of 7 days	

Table 3.2 Dose Reduction Steps for Vorinostat-Specific Related Toxicities

If the phase I lead in portion determines that the phase II vorinostat dose is 300mg daily the following table will be used for vorinostat dose modifications.

Starting Dose	1st dose reduction	2nd dose reduction	3rd Dose Reduction
Vorinostat	Vorinostat	Vorinostat	Discontinue therapy
3 capsules – 300 mg	2 capsules – 200 mg	1 capsules – 100 mg	
OR	OR	OR	
6mL of 50mg/mL	4mL of 50mg/mL	2mL of 50mg/mL	
suspension	suspension	solution	
5 out of 7 days	5 out of 7 days	5 out of 7 days	

Any of the following will necessitate vorinostat dose modification:

1. Grade 4 non-hematologic toxicity (not laboratory)

2. Grade 3 non-hematologic toxicity (not laboratory) lasting >3 days despite optimal supportive care.

- 3. Any Grade 3 or Grade 4 non-hematologic laboratory value if:
 - Medical intervention is required to treat the patient, or
 - The abnormality leads to hospitalization

4. Grade 3 or Grade 4 febrile neutropenia:

Grade 3 is defined as ANC <1000/mm3 with a single temperature of >38.3 degrees C (101 degrees F) or a sustained temperature of \geq 38 degrees C (100.4 degrees F) for more than one hour

Grade 4 is defined as ANC <1000/mm3 with a single temperature of >38.3 degrees C (101 degrees F) or a sustained temperature of \geq 38 degrees C (100.4 degrees F) for more than one hour, with life-threatening consequences and urgent intervention indicated.

- 5. Prolonged delay (>2 weeks) in initiating cycle 2 due to treatment-related toxicity
- 6. Hematologic or gastrointestinal toxicity that mandates dose modification according to Section 5.2.1.4

5.2.1.4 Dose modification and supportive care for specific toxicities related to Vorinostat & MK-3475

5.2.1.4.1 Hematologic Toxicity

1. Neutropenia

Grade 3 (ANC $\ge 0.5 - 1.0 \times 10^9$ /L) Continue MK-3475 and Vorinostat dosing and maintain dose level.

Grade 4 (ANC less than 0.5 x 10^9 /L) Hold MK-3475 and vorinostat until ANC recovery to 1.0 x 10^9 /L. Dose adjustment according to Table 3.2 and 3.3. is mandatory.

To follow Grade 4 neutropenia, ANC values should be obtained per institutional guidelines; re-dosing decision may be made on local laboratory values. Duplicate samples should be sent to the central laboratory, whenever possible.

2. Anemia

Grade 3 (hemoglobin $\geq 6.5 - 8.0$ g/dl): Continue MK-3475 and Vorinostat dosing and maintain dose level..

Grade 4 (hemoglobin less than 6.5 g/dl)

Hold MK-3475 and vorinostat until hemoglobin recovery to ≥ 8.0 g/dl. Supportive care and transfusion support per institutional guidelines should be implemented. Dose adjustment according to Table 3.2 and 3.3. is mandatory..

To follow Grade 4 anemia, Hgb values should be obtained per institutional guidelines; re-dosing decision may be made on local laboratory values. Duplicate samples should be sent to the central laboratory, whenever possible.

3. Thrombocytopenia

Grade 3 (platelet value >25,000 – 50,000/ μ L. Continue MK-3475 and Vorinostat dosing and maintain dose level..

Grade 4 (platelet value 25,000 µL or less)

Hold both MK-3475 and vorinostat (for up to 2 weeks) until platelet recovery to $>50,000/\mu$ L has been observed with or without platelet transfusion. Dose adjustment according to Table 3.2 and 3.3. is mandatory.

To follow Grade 4 thrombocytopenia, platelet values should be obtained per institutional guidelines; re-dosing decision may be made on local laboratory values. Duplicate samples should be sent to the central laboratory, whenever possible.

4. Lymphopenia

Dose interruption or study discontinuation is not required for lymphopenia of any grade.

5.2.1.4.2 Gastrointestinal Toxicity

1. Diarrhea

Grade 3 or Grade 4 diarrhea: Hold MK-3475 and Vorinostat until resolution to Grade 1 or less, or to baseline. Dose modification for the two drugs will be followed as outlined by Tables 3.1 and 3.2

Some patients will experience diarrhea following vorinostat or the combination, mildto-moderate in severity. To date, observation of diarrhea has tended to increase in frequency with continued dosing; both site personnel and patients should be told of the possibility of increased diarrhea with continued cycles.

All subjects who experience diarrhea should be advised to drink liberal quantities of clear fluids. If sufficient oral fluid intake is not feasible, fluid and electrolytes should be substituted via IV infusion.

Diarrhea should be managed aggressively, as Grade 2 Diarrhea may progress to Grade 3, necessitating interruptions in therapy. Consideration regarding use of prophylactic and/or supportive care should be made upon the first observation of

Grade 1 or higher Diarrhea. Non-prescription methods to improve diarrhea include: diet modification (increased fiber, certain brands of yogurt, such as Probiotics), and hydration. Anti-diarrheal prescriptions medications include: loperamide and diphenoxylate with atropine. Consider giving the patient a prescription for an antidiarrheals to be filled if needed on the first day of therapy.

2. Enterocolitis

Subjects should be carefully monitored for signs and symptoms of enterocolitis (such as diarrhea, abdominal pain, blood or mucus in stool, with or without fever) and of bowel perforation (such as peritoneal signs and ileus). In symptomatic subjects, infectious etiologies should be ruled out, and if symptoms are persistent and/or severe, endoscopic evaluation should be considered.

In subjects with severe enterocolitis (Grade 3), MK-3475 will be permanently discontinued and treatment with systemic corticosteroids should be initiated at a dose of 1 to 2 mg/kg/day of prednisone or equivalent. When symptoms improve to Grade 1 or less, corticosteroid taper should be started and continued over at least 1 month.

In subjects with moderate enterocolitis (Grade 2), MK-3475 should be withheld and anti-diarrheal treatment should be started. If symptoms are persistent for more than one week, systemic corticosteroids should be initiated (e.g., 0.5 mg/kg/day of prednisone or equivalent). When symptoms improve to Grade 1 or less, corticosteroid taper should be started and continued over at least 1 month. Regarding guidelines for continuing treatment with MK-3475, see Section 5.2. Additional data regarding management of this immune related adverse event will be included in Appendix 12.8

3. Nausea/Vomiting/Dehydration

Grade 3 Nausea/Vomiting/Dehydration lasting >72 hours despite aggressive supportive care OR **Grade 4** Nausea/ Vomiting/Dehydration(lasting any duration) will result in stepwise dose reduction as outlined in Tables 3.1. and 3.2. Until resolution of the toxicity to Grade 1 or less or to baseline, MK-3475 and vorinostat are to be held.

Supportive care for Nausea/Vomiting: Some patients will experience nausea following vorinostat or the combination, generally mild-to-moderate in severity. With subsequent cycles, many patients note that the sensation of nausea becomes less. Once documented nausea and/or vomiting has been observed, the use of antiemetics per institutional guidelines is strongly encouraged. Non-prescription methods to improve nausea include: antacids, antiulcer drugs, ginger ale or ginger lozenges. Encourage each patient to drink at least 2 liters of fluid each day to avoid dehydration. Anti-emetic prescriptions medications include: prochlorperazine, lorazepam, or any of the 5-HT3 reuptake inhibitors (granisetron; ondansetron; palonosetron; dolasetron; or tropisetron). Consider giving the patient a prescription for an anti-emetics to be filled if needed on the first day of therapy.

Dehydration should be managed with aggressive hydration (either intravenous or oral fluids). Patients should be strongly encouraged to maintain significant oral fluid intake.

5.2.1.5 Initiation of subsequent cycles of therapy:

- MK-3475 and vorinostat are to be started on the same day. If an increase in MK-3475 dosing interval is required according to Table 3.1, vorinostat will be taken 5 out of 7 days for every week of the MK-3475 dosing interval.
- A new course of treatment may begin on the scheduled Day 1 of a new cycle if all non-hematological toxicity from the previous cycle has recovered to ≤ Grade 1 or baseline, and/or hematologic recovery documented as outlined in section 5.2.1.4.

Initiation of subsequent cycles of therapy may be delayed for up to 12 weeks to allow recovery from all drug-related toxicity. Alternately, the Investigator may choose to administer supportive care (blood product transfusions) for retreatment criteria to be met. If the recovery criteria are not met after a 12-week delay, the patient will be discontinued from study treatment unless, in the opinion of the Investigator, the patient is experiencing a clinical benefit, in which case a decision regarding continuation of treatment will be made on an individual patient basis in consultation with the Merck medical monitor. Justification will be recorded in the source documents.

When initiating a subsequent cycle, a minimum interval of 21 days should be observed between MK-3475 administrations (with no minimum interval for vorinostat).

Continuation of study therapy during a cycle:

Within any cycle, the dose/schedule of either study drug may be adjusted as necessary.

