5.2.1.2 Dose Modifications for MK-3475 and Vorinostat

Toxicity will be graded using Common Terminology Criteria for Adverse Events (CTCAE version 4.0). The protocol will change to CTCAE version 5.0 if is published within the course of the trial.

Because it there may be overlap in the toxicities of both agents, and difficulty in attributing toxicity to either agent, patients experiencing any Grade 3 toxicity (except those outlined in Table 3.1 and Section 5.2.1.4) or any Grade 4 toxicity will have *both MK-3475 and vorinostat held until improvement of the adverse event to Grade 1 or baseline*.

Toxicity that requires more than two dose reductions or modifications of vorinostat will lead to discontinuation of the patient from the treatment phase of the study. *Patients are not permitted to continue on vorinostat or MK-3475 dosing alone.* In addition, no dose re-escalations are allowed during the study period unless toxicities are resolved to grade 1. Justification will be recorded in the source documents

Before initiation of subsequent cycles, each patient will be evaluated for possible toxicities that may have occurred after the previous treatment. All Grade 3 or 4 toxicities

(except those specified in Table 3.1 and Section 5.2.1.4) should resolve to Grade 1 or baseline before re-initiation of study treatment. Dose modification will be made based on the toxicity with the greatest severity.

Toxicity	Grade	Hold Treatment (Y/N)	Timing for restarting treatment	Dose/Schedule for restarting treatment	Discontinue Subject (after consultation with Sponsor)
Hematological Toxicity	1, 2	No	N/A	N/A	N/A
	3* *Excluding Grade 3 neutropenia, anemia, and thrombocytopenia See Section 5.2.1.4)	Yes	Toxicity resolves to Grade 0-1 or baseline	May increase the dosing interval by 1 week	Toxicity does not resolve within 12 weeks of last infusion Permanent discontinuation should be
	4	Yes	Toxicity resolves to Grade 0-1 or baseline	May increase the dosing interval by 1 week	considered for any severe or life-threatening event
Non-hematological toxicity	1	No	N/A	N/A	N/A

Toxicity	Grade	Hold Treatment (Y/N)	Timing for restarting treatment	Dose/Schedule for restarting treatment	Discontinue Subject (after consultation with Sponsor)

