 Note: Exception to be treated similar to grade 1 toxicity Grade 2 alopecia Grade 2 fatigue For additional information regarding Adverse Events with a potential Immune-Etiology reference Section 5.6.1.1. and Appendix 12.8 	2	Consider withholding for persistent symptoms	Toxicity resolves to Grade 0-1 or baseline	Clinical AE resolves within 4 weeks: Same dose and schedule (reference Section 5.6.1.2 for recommendations regarding pneumonitis) Clinical AE does not resolve within 4 weeks: May increase the dosing interval by 1 week for each occurrence	Toxicity does not resolve within 12 weeks of last infusion
	3, 4	Yes	Toxicity resolves to Grade 0-1 or baseline	May increase the dosing interval by 1 week for each occurrence	Toxicity does not resolve within 12 weeks of last infusion Permanent discontinuation should be considered for any severe or life-threatening event

In case toxicity does not resolve to Grade 0-1 within 12 weeks after last infusion, trial treatment should be discontinued. With investigator and Sponsor agreement, subjects with a laboratory adverse event still at Grade 2 after 12 weeks may continue treatment in the trial only if asymptomatic and controlled. For information on the management of adverse events, see Section 5.6.1.

Subjects who experience a recurrence of the same severe or life-threatening event at the same grade or greater with re-challenge of MK-3475 should be discontinued from trial treatment.

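### Section 5.2.1.4.2 requires a permanent MK-3475 stop for Grade 3 enterocolitis but does not name Grade 4, which by the letter of the protocol body falls under a hold-and-restart rule

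*Combined protocol and SAP*

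**What the plan says.** The enterocolitis item in Section 5.2.1.4.2 sets rules for two grades. For the severe grade: "In subjects with severe enterocolitis (Grade 3), MK-3475 will be permanently discontinued", with systemic corticosteroids. For the moderate grade: "In subjects with moderate enterocolitis (Grade 2), MK-3475 should be withheld and anti-diarrheal treatment should be started". Grade 4 is not mentioned. The item sends the reader to Section 5.2 on whether MK-3475 may continue, and adds: "Additional data regarding management of this immune related adverse event will be included in Appendix 12.8". That appendix, the guidance on events of clinical interest, appears in the available documents by title only.

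The general rules are in Section 5.2.1.2, and the hold statement is repeated in Section 5.2.1.3. Patients with "any Grade 3 toxicity (except those outlined in Table 3.1 and Section 5.2.1.4) or any Grade 4 toxicity will have" both drugs held until the event is back to Grade 1 or baseline. In Table 3.1, the non-hematological row for Grades 3 and 4 allows restart at Grade 0-1 or baseline, if wanted with a dosing interval one week longer. It provides for a stop if the event has not resolved within 12 weeks of the last infusion, and then says: "Permanent discontinuation should be considered for any severe or life-threatening event". Section 5.2.1.2 also rules out single-agent treatment: "Patients are not permitted to continue on vorinostat or MK-3475 dosing alone".

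**The concern.** A toxicity rule should not become more lenient as the event becomes worse. Here the mandatory permanent stop is tied to Grade 3 alone, and the text that covers Grade 4 is a hold with restart on recovery. Table 10 defines Grade 4 as life-threatening. A clinician who follows the words exactly could re-challenge a patient after a resolved Grade 4 event but not after a resolved Grade 3 event.

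Section 4.2.3 says that there is no reported clinical experience with the combination, and safety and tolerability are the primary objective. What is at stake is the protection of a patient who has such an event. No estimate or test in the trial is at stake.

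**Working it through.** No arithmetic applies. The check sets the enterocolitis item beside each rule that could reach Grade 4.

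**1. What the rules say, grade by grade**

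| Enterocolitis grade | Section 5.2.1.4.2 | General rule | Explicit rule for MK-3475 at a first event that resolves in time |
|---|---|---|---|
| 2 | Withhold | Table 3.1: consider withholding | Withhold; restart possible |
| 3 | Permanent stop | General hold yields to Section 5.2.1.4 at Grade 3 | Permanent stop |
| 4 | Not named | Hold both drugs; restart at Grade 0-1 or baseline | Hold; permanent stop to be considered |

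**2. Is Grade 4 left open, or covered by another rule?** It is covered. In the hold statement of Sections 5.2.1.2 and 5.2.1.3, the exception for Section 5.2.1.4 attaches to Grade 3 toxicities; Grade 4 follows without an exception. The later statement in Section 5.2.1.2, on restarting after an event of either grade, reads in part: "except those specified in Table 3.1 and Section 5.2.1.4) should resolve to Grade 1 or baseline before re-initiation of study treatment". It exempts only what Section 5.2.1.4 specifies, and Grade 4 enterocolitis is not specified there. Section 5.2.1.3 also lists a Grade 4 non-hematologic toxicity as a trigger for a vorinostat dose modification, so continuing after a Grade 4 event is foreseen.

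**3. How do neighbouring items treat Grade 4?** In the same section, "Grade 3 or Grade 4 diarrhea" is one category with a hold rule, and nausea, vomiting and dehydration have a Grade 4 rule. In Section 5.2.1.4.1, neutropenia, anemia and thrombocytopenia each have a Grade 4 rule, and lymphopenia is covered at every grade. Tables 5 (infusion reactions) and 7 (pneumonitis) apply discontinuation to Grades 3 and 4 together. Enterocolitis is the exception.

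**4. What stands between a first Grade 4 event and re-challenge?**

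- Section 5.6.1.1: immune-related events of Grade 2 or higher are discussed at once with the Sponsor. The discontinuation column of Table 3.1 also provides for Sponsor consultation.
- Section 7.2.3.2: colitis of Grade 3 or higher is reported to the Sponsor within 24 hours.
- Table 10: re-challenge after a serious event that may be drug-caused needs advance approval by the U.S. clinical monitor. A Grade 4 event is serious because it is life-threatening. The approval is to follow the protocol's dose modification guidelines, which is the text that lacks the Grade 4 rule.
- Section 5.2.1.2: stop if the event has not resolved within 12 weeks. Section 5.2.1.5 allows a clinical-benefit exception to the 12-week limit on cycle delay, in consultation with the Merck medical monitor.
- Section 5.2.1.2: stop if the event recurs at the same or a higher grade on re-challenge.
- Sections 2.1.2 and 5.8: unacceptable adverse events end treatment. Section 5.8 defines these by reference to Section 5.2.1.2.

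These make an unconsidered re-challenge unlikely. None expressly requires a stop at a first Grade 4 event that resolves in time.

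**5. Does Table 6 settle it?** No. It covers immune-related events not detailed elsewhere in the protocol, and enterocolitis is detailed in Section 5.2.1.4.2.

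**The case against.** The strongest objection is that Appendix 12.8 may already contain a Grade 4 rule. The enterocolitis item cites it directly, and other sections rely on the same guidance. This stands as a limit: the point can be made only for the protocol body. Even if the appendix requires a stop, Sections 5.2.1.2 and 5.2.1.3 would still give a conflicting hold rule for every Grade 4 toxicity.

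Second, a sensible clinician will read the Grade 3 rule as a minimum. Tables 5 and 7 support that reading, and it is probably the intent. The text does not say so, and the general rule tells a literal reader something else.

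Third, the gap may largely close itself. Section 7.2.4 requires each change of grade within an episode to be recorded, so a Grade 4 case that passes through Grade 3 while worsening or recovering would arguably trigger the Grade 3 stop. This is an inference, but a fair one. A case recorded as going straight to Grade 4 and then to Grade 2 or lower would escape it.

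A reader might infer that the trial leaves life-threatening enterocolitis without a rule, or allows re-challenge freely. The documents do not support that: a hold is mandatory, and the safeguards listed in the working apply before any restart.

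**Conclusion.** The point holds for the protocol body. Grade 3 enterocolitis carries a mandatory permanent stop of MK-3475. A first Grade 4 event that resolves in time carries a mandatory hold, with a permanent stop only to be considered. The conclusion rests on a literal reading and on Appendix 12.8 being unavailable.

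The practical size is small. The affected case is a Grade 4 event never recorded at Grade 3, resolved within the limit, with re-challenge discussed and approved. The documents give no rate of Grade 4 enterocolitis, so the number of patients cannot be stated.

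It would be wrong to infer that the safety endpoint or the run-in decision is compromised. A related Grade 4 non-hematologic, non-laboratory toxicity in Cycle 1 is a DLT under Section 2.1.1.1 whatever the later treatment decision. This is a minor safety-wording correction with no effect on endpoints, DLT rules, sample size or analysis.

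**What to change.** First compare the protocol with Appendix 12.8. Then make two changes in Section 5.2.1.4.2:

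1. Extend the Grade 3 enterocolitis sentence to severe or life-threatening enterocolitis, Grade 3 or Grade 4.
2. State that this rule takes precedence over the hold statement for Grade 4 toxicities in Section 5.2.1.2 and its repeat in Section 5.2.1.3. The later statement in Section 5.2.1.2 needs no change, because its exemption will cover Grade 4 enterocolitis once Section 5.2.1.4.2 names it.

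Optionally, add that Grade 3 or 4 diarrhea diagnosed as enterocolitis follows the enterocolitis rule. Diarrhea is a listed sign of enterocolitis and has a hold rule of its own. This is clarification only, since the enterocolitis item applies by its own terms once that diagnosis is made.

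The cost is a changed phrase and one added sentence in an amendment, with no new data or visits. The downside is that a rare patient who recovers from Grade 4 enterocolitis loses the option of re-challenge and, because single-agent treatment is barred, also stops vorinostat. The protocol already accepts that loss at Grade 3.

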5.2.2. Timing of Dose Administration

Vorinostat and MK-3475 dose will both be initiated on day 1 of each treatment cycle after all procedures/assessments have been completed as detailed on the Trial Flow Chart (Section 6.0). Trial treatment may be administered up to 3 days before or after the scheduled Day 1 of each cycle due to administrative reasons.

All trial treatments will be administered on an outpatient basis.

Oral vorinostat (400 mg) administered is once daily by mouth with food or within 0-30 minutes after a meal (if possible) for days 1-5 of each week in a week (21 day) treatment cycle. For any patient experiencing Grade 1 or higher drug-related fatigue, the Investigator should advise the patient to administer vorinostat prior to bedtime (See Section 3.2.6.3). On the day that MK-3475 is administered patient should take vorinostat a minimum of 2 hours before the MK-3475 infusion.

For patients unable to swallow pills, vorinostat will be administered as a 50mg/mL suspension. This solution will be prepared by investigational pharmacy and administered via gastrostomy tube or nasogastric tube. Gastrostomy tubes will be flushed with 20 mL of water before and after the suspension is administered. The dosing and dose reductions will follow Table 3.2.

MK-3475 will be administered as a 30 minute IV infusion (treatment cycle intervals may be increased due to toxicity as described in Section 5.2.1.2). Sites should make every effort to target infusion timing to be as close to 30 minutes as possible. However, given the variability of infusion pumps from site to site, a window of -/+10 minutes is permitted (i.e., infusion time is 30 minutes: -/+10 min).

